All participants will provide demographic information at baseline and will have height and weight measured. To determine acceptability (Aim 2a), we will use the SUS and USE. Those randomly assigned to VR will also complete the PQ. To examine motivation to make behavior change (Aim 2b), participants will complete measures assessing self efficacy³⁹ and readiness to change behavior.⁴⁰ Specifically, they will complete the 16-item Self-Efficacy for Healthy Eating and Physical Activity measure⁴¹ and self-efficacy to lose weight will be assessed with the 8-item Weight Efficacy Lifestyle Questionnaire.^{42,43} Readiness to change behavior will be measured by the 6-item Readiness to Change Diet and Physical Activity Scale.⁴⁴ To examine behavioral beliefs and intentions (Aim 2c), participants will complete measures of behavioral cognitions from the Theory of Planned Behavior, including behavioral beliefs, attitudes, and intentions related to eating an activity behaviors.^{45,46} Finally, to examine behavior (Aim 2d), participants will complete self-report measures of activity and eating behavior over the past week, adapted from the Health Behavior in School-aged Children survey⁴⁷ at baseline and 2-week follow-up. The 10-item Positive and Negative Affect Schedule for Child and Parent⁴⁸ will be administered to control for mood and the child emotional eating scale serves as a measure of emotion regulation. Body esteem will be measured with several items from the Body Esteem Scale.^{49,50}

E. Study Design

E1. Overview or Design Summary

Study 2 will use a randomized pilot trial design to compare the VR experience to a video (created by team at WUSM) that provides child-friendly education on what types of foods are most nutritious and which are less healthy, and how the food they eat and activity they engage in now affects their health and future. The video will also encourage consideration of future consequences.

E2. Subject Selection and Withdrawal

E2.A. Inclusion Criteria

1. Parent is biological or legal guardian and can therefore consent on behalf of the child
2. Parent BMI is greater than or equal to 25 (overweight or obese)
2. Parent is under 80 years old and child is between 6 and 12 years old
3. Child BMI is at or above the 85th percentile for age and sex.⁵¹

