For individuals participating in the pilot study, there may be no direct benefits in terms of addressing overweight or obesity. However, individuals participating may benefit from knowing that their feedback is helping to design a digital tool that may ultimately address childhood obesity.

E2.G. Early Withdrawal of Subjects

Informed consent will make clear that participants may withdraw at any time with no penalty.

E2.H. When and How to Withdraw Participants

Taking part in this research study is voluntary. Participants may choose not to take part in this research study or may withdraw their consent at any time. They may withdraw by telling the research team they are no longer interested in participating in the study. If participants do not respond to phone calls or emails after 6 attempts to contact, they will be withdrawn from the study. Additionally, there will be 6 attempts to contact participants for the 2 week follow-up surveys via email or phone. There will be no penalty or loss of benefits to which they were otherwise entitled.

E2.I. Data Collection and Follow-up for Withdrawn Subjects

When a participant withdraws from the study, the research team will stop collecting data from them.

F. Study Procedures

F1. Screening for Eligibility

Eligibility will be assessed using the phone eligibility screen.

F2. Schedule of Measurements

Construct	Measure(s)	Participant(s) Taking	Time point
Eligibility			
Screen for disordered eating behaviors	Selected and Adapted Questions from ChEDE-Q	Parent self and proxy-report	Phone screen
Screen for overweight and conditions that could make it unsafe to participate in VR condition	Other Eligibility Questions In-lab height & weight	Parent self and proxy-report Parent & Child	Phone screen Pre
1. Acceptability (Aim 2a)			
Usability	System Usability Scale	Parent proxy-report	post
	Selected Child Interview Questions	Child self-report	
Ease of Use	Usefulness, Satisfaction and Ease of Use	Parent proxy-report	
	Selected Child Interview Questions	Child self-report	
Degree of immersion (for those in VR condition)	Presence Questionnaire	Parent self-report	
	Selected Child Interview Questions	Child self-report	
1. Motivation to Change behavior (Aim 2b)			
Self-Efficacy	Self-Efficacy for Healthy Eating and Physical Activity (SE-HEPA)	Child self-report,	Pre & post
Readiness to Change Behavior	Readiness to Change Diet and Physical Activity Scale	Parent self-report	Pre and post or 2-weeks depending on each question

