BehaVR (<https://behavr.com>) is a HIPAA-compliant company focused on building VR products for behavior change and has a dedicated and talented team of software engineers. BehaVR will host the proposed VR experience and all data collected within the VR experience. Prior to beginning this study, BehaVR and Washington University will enter into a Business Associate and Qualified Service Organization agreement. BehaVR will comply with the rules on handling of Protected Health Information under HIPAA.

Training: All staff personnel are trained and comply with HIPAA regulations. All study team members will complete the CITI training and Good Clinical Practice training.

Performance Monitoring: The Data and Safety Monitoring Plan for this trial includes close monitoring by the PI. Any adverse event will be reported promptly to the IRB.

H. Study Administration

H.1. Funding Source and Conflicts of Interest

This study is funded by the Washington University Center for Diabetes Translation Research, which is funded by the NIDDK. Any potential financial conflicts of interest for individual research team members are reported according to the IRB requirements and procedures.

H.2. Participant Payment

Participants will each receive a \$25.00 gift card for completing the in-lab visit and a \$25.00 gift card for completing the two week follow-up survey as well as a chance to win one of two \$250 gift cards via a raffle.

I. References

1. Centers for Disease Control and Prevention. Overweight and obesity. 2018 [Available from: <https://www.cdc.gov/obesity/>].

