Univariate analyses of variance (ANOVA) models evaluated pre- to post-test changes in positive and negative affect by condition. T-tests evaluated the difference in acceptability measures between conditions. Repeated-measures general linear models, with time as the within-subjects factor, tested the effect of the VR intervention on eating and activity behaviors (pre to two-weeks) and cognitions (pre to post). Child age was included as a covariate in all analyses. Tests of normality were conducted on dependent variables across and within conditions using histograms, normality plots, skewness, and kurtosis metrics, and relevant dependent variables were transformed (e.g., cubed) when necessary. Assumptions of linearity and homogeneity of regression slopes were examined with scatterplots and interaction terms of condition and the relevant pre-test variable.

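### Two-week behaviour is tested as a change score in families with both surveys; conditioning on baseline would be more precise and would remove one form of non-response bias

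*Combined protocol and SAP*

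**What the plan says.** Section J (Statistical Analysis Plan): "Repeated-measures general linear models, with time as the within-subjects factor, tested the effect of the VR intervention on eating and activity behaviors", from pre-test to two weeks. It adds: "Child age was included as a covariate in all analyses". The pre-test value of the outcome is not named as a covariate. The section ends with a check that regression slopes are equal across arms, using products of condition and the relevant pre-test score, but does not say which models this belongs to.

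Section D2 places the behaviour measures "at baseline and 2-week follow-up". The schedule in F2 also allows some readiness-to-change items (Aim 2b) to be taken at two weeks.

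On non-response, E2.H says "If participants do not respond to phone calls or emails after 6 attempts to contact, they will be withdrawn from the study" and then "Additionally, there will be 6 attempts to contact participants for the 2 week follow-up surveys via email or phone". E2.I says "When a participant withdraws from the study, the research team will stop collecting data from them". H.2 provides a "gift card for completing the two week follow-up survey".

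The documents state no analysis population, missing-data method, expected dropout or sensitivity analysis for the two-week outcomes.

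**The concern.** A standard repeated-measures GLM needs every time point. With only two, a family without the two-week survey contributes nothing, and its baseline data are discarded. Among the remaining families the test compares mean change, which fixes the coefficient on baseline at 1 instead of estimating it.

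This has two consequences. Precision is lost whenever the pre/two-week correlation is below 1. And if the families lost from one arm differ at baseline from those lost from the other, regression to the mean differs between arms and appears as a treatment effect. Aim 2d is an efficacy aim meant to inform later grant applications, so both the estimate and its precision matter, even in a pilot.

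**Working it through.** **Inputs.** From the documents: 60 child-parent pairs (E2.D), families randomised after baseline (E2.E), behaviour measured at two time points, child age as covariate (J). The figure of 60 has no derivation, so there is no calculation to reproduce. Assumed: 1:1 allocation (30 per arm), SD 1, correlation ρ of 0.5 or 0.7, no true effect, 18% or 28% missing, log-odds of non-response 1 per SD of baseline.

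**Step 1: what the model tests.** In a simulated data set of 60 families with 9 two-week values missing, the repeated-measures time-by-condition test with age as covariate was set beside a regression of change on arm and age. Both used 51 families and gave F = 0.0876, p = 0.769. They are the same test.

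**Step 2: precision, no missing data.**
- Change score: SE = √(2(1−ρ)) × √(2/30). At ρ = 0.5: 1.000 × 0.258 = 0.258. At ρ = 0.7: 0.775 × 0.258 = 0.200.
- Conditioning on baseline: SE = √(1−ρ²) × √(2/30). At ρ = 0.5: 0.866 × 0.258 = 0.224. At ρ = 0.7: 0.714 × 0.258 = 0.184.
- Ratio = √((1+ρ)/2): 0.866 at ρ = 0.5 (13% smaller) and 0.922 at ρ = 0.7 (8% smaller).

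**Step 3: bias when loss depends on baseline in one arm.** Let B be baseline and Y the two-week value. Since E(Y|B) = ρB, the mean change among those kept in that arm is −(1−ρ) × E(B | kept). The other arm loses families at random and contributes 0. Integrating the logistic non-response curve over a standard normal baseline, with lower values lost more often, gives E(B | kept) = 0.157 at 18% missing and 0.237 at 28%.

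| Missing | Bias, ρ = 0.5 | Bias, ρ = 0.7 |
|---|---|---|
| 18% | 0.5 × 0.157 = 0.08 | 0.3 × 0.157 = 0.05 |
| 28% | 0.5 × 0.237 = 0.12 | 0.3 × 0.237 = 0.07 |

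These are sizes in SD; the sign follows the direction of the selection. A large simulation agrees: 0.086 and 0.122 at 20% and 30% missing for ρ = 0.5. Conditioning on baseline gave 0.000 and 0.003 in the same runs.

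**Step 4: bias against noise.** With 18% and 28% missing, 24.6 and 21.6 families per arm remain. The change-score SE is √(2/24.6) = 0.29 and √(2/21.6) = 0.30 at ρ = 0.5, and 0.775 times these, 0.22 and 0.24, at ρ = 0.7. Every bias in the table is less than half its SE.

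**Step 5: other patterns of loss.**
- Random loss, including 30% in one arm and 10% in the other: bias about 0.
- Equally selective loss in both arms: the two terms cancel, bias 0.
- Opposite selection in the two arms: the terms add, giving 2 × 0.079 = 0.16 and 2 × 0.119 = 0.24 at ρ = 0.5, still below the SE.
- Loss in one arm dependent on the unseen two-week value, ρ = 0.5: change score 0.09 and 0.12 at 20% and 30% missing; baseline-adjusted 0.13 and 0.19. Adjustment does not help here.
- VR-arm loss dependent on post-session intention: change score 0.04, complete-case ANCOVA 0.06, imputation that uses the post-session score 0.00.

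**Step 6: post-session scores as covariates.** With no missing data and an effect of 0.20 that acts wholly through post-session cognition, adding that score to the outcome model cut the estimated effect to 0.00.

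**The case against.** **Section J may already adjust for baseline.** The check on regression slopes is an ANCOVA check and suggests that pre-test values entered some models. This stands in part: if the behaviour models conditioned on baseline, the bias in step 3 and the precision loss largely disappear. But age is the only covariate named, and the text does not say which models the check served.

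**The withdrawal rule.** A reader might infer from E2.H and E2.I that non-responders are removed from the Aim 2d analysis by rule. The documents do not say so. The withdrawal sentence is general, the sentence on the two-week survey does not state what follows a sixth failed attempt, and E2.I stops collection without deleting data. The two-week value is missing either way, so these sections add little.

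**Is differential loss likely?** Sections E2.F describes nausea and negative affect as possible in VR, which makes arm-specific loss conceivable. Nothing shows that families put off by a condition are those who fail to reply. Follow-up is a survey, not a visit, and six contact attempts and a gift card should limit loss. They do not say how any remaining loss is analysed.

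**It is a pilot of 60.** True, and sampling error exceeds the bias. But D1 states an efficacy aim, and the precision gain does not depend on any missing data.

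**Conclusion.** The concern holds in limited form. As written, the two-week behaviour model is a change-score test in families with both surveys. With 60 families it gives a standard error of about 0.26 SD where baseline adjustment gives 0.22 (ρ = 0.5), or 0.20 against 0.18 (ρ = 0.7). It can be biased by about 0.08-0.12 SD (ρ = 0.5) or 0.05-0.07 SD (ρ = 0.7) if non-response depends on baseline in one arm only. Every rate, correlation and selection strength is assumed; the documents give none.

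A reader might go further and infer that the completer comparison is biased. The documents do not support that: there is no bias under random or equally selective loss, and the largest figure, 0.24 SD, needs opposite selection in the two arms, for which they give no reason. Nor is Aim 2d the only outcome exposed: readiness items taken at two weeks and the exploratory indirect effects (Aim 2e) also need two-week data.

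**What to change.** In Section J, for the two-week outcomes (Aim 2d behaviour and any readiness items taken then):

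- Analyse all randomised families in their assigned arm, keeping data collected before any withdrawal.
- Use a baseline-adjusted model with arm and child age: ANCOVA, or a mixed model with a common baseline mean, which is justified because randomisation follows baseline. ANCOVA alone still omits families without a survey, so pair it with multiple imputation.
- If imputing, use post-session cognition scores only as imputation predictors and never as covariates in the outcome model, because they are the hypothesised mediator in Aim 2e.
- State which models the regression-slopes check applies to.
- Report two-week completion by arm, and add one sensitivity analysis that shifts imputed values by arm, since baseline adjustment does not protect against loss that depends on the two-week value itself.

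No new data are needed. The cost is SAP wording and modest programming, or a re-analysis if the past tense of Section J means the models have been run. The main analysis would rest on a stated missing-at-random assumption, which the sensitivity analysis probes.
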